5.13.6.1 Continuous ECG Monitor

- Each subject will be provided with a 24-hour continuous ECG monitor and will be instructed in its use.
- The monitoring service will be available to provide any necessary assistance with the use of the device and to reinforce the need to adhere to the protocol for the full 24 hours.

If a subject has symptomatic AF at the end of the 6-month follow-up visit, an event monitor will be provided to be used up to the 12-month follow-up visit to capture AF episodes.

5.13.7 12 Month Follow-Up

Subjects will return for an office visit 6 months (180 days ± 30 days) postablation treatment. At a minimum, the following data will be collected at 6 months:

- Use, changes in or discontinuation of anticoagulation, rate control and/or antiarrhythmic medications;
- Cardioversions since last visit:
- Any additional ablation procedures performed;
- For subjects on anticoagulants, assessment of INR/PTT therapeutic levels (maintain as clinically indicated);
- Cardiac rhythm as determined by a 12-lead ECG at the time of the visit;
- Heart failure status as assessed by NYHA classification at the time of visit:
- Cardiac rhythm as determined by a 24-hour continuous ECG monitor following the visit for subjects in NSR at the time of the visit;
- Any hospital readmissions, including admission and discharge dates, since the previous visit; and
- Adverse events.

5.13.7.1 Continuous ECG Monitor

- Each subject will be provided with a 24-hour continuous ECG monitor and will be instructed in its use.
- The monitoring service will be available to provide any necessary assistance with the use of the device and to reinforce the need to adhere to the protocol for the full 24 hours.
- If a subject has symptomatic AF at the end of the 6-month follow-up visit, an event monitor will be provided to be used up to the 12-month follow-up visit to capture AF episodes.

5.13.7.2 Electro-anatomical mapping

The pre-ablation mapping will be performed using either the Rhythmia System and Orion Catheter (Boston Scientific, Natick Massachusetts USA) or the CARTO System and Penta-Ray Catheter (Biosense Webster, Diamond Bar California USA). These systems and their accessory devices (mapping catheters and ECG patches) bear a CE mark. The mapping procedure will begin with femoral venous access and introduction of a CE marked transseptal sheath and needle (e.g., Agilis, St. Jude Medical, St. Paul Minnesota USA) to gain access to the left atrium. The mapping catheter will be introduced and used to collect baseline electrograms (EGMs) and demonstrate electrical communication of the pulmonary veins to the left atrium. An electro-anatomical map will be created and the diagnostic catheters will be withdrawn. This same process will be before and after ablation.

5.14 Unscheduled Visit

Any unscheduled follow-up visits that occur throughout the trial, other than routine follow-up visits per the institution's or investigator's normal standard of care, shall be documented. At the minimum, the following data will be collected:

- Use, changes in or discontinuation of anticoagulation, rate control and/or antiarrhythmic medications;
- Cardioversions since last visit:
- Any additional ablation procedures performed;
- For subjects on anticoagulants, assessment of INR/PTT therapeutic levels (maintain as clinically indicated);
- Cardiac rhythm as determined by a 12-lead ECG at the time of the visit;
- Heart failure status as assessed by NYHA classification at the time of visit;
- Any hospital readmissions, including admission and discharge dates, since the previous visit; and
- Adverse events.

5.15 Study Exit or Premature Withdrawal

Once the subject has completed the final follow-up visit they can be exited from the trial provided that they do not have any conditions that require continued follow-up.

5.16 Summary of Trial Assessments

Table 4: Summary of Trial Assessments

Assessment	Baseline	Procedure	30 Days Post- Procedure/ Discharge*	3 Month (End of Blanking Period)	6 Month	12 Month	Unscheduled
Visit Timeframe (days)			30±7	90±14	180±30	365±30	-
Medical History	Х						
Medication History (current)	Х						
Medications		Х	Х	X	Х	Х	Х
Pregnancy test (for females of childbearing potential)	Х			X			
12-lead ECG	Х		X	Х	Х	Х	Х
24-Hour Continuous ECG Monitor (e.g., Holter)					Х	Х	
Cardiac CT or MRI	Х			Х			
3D Electro-anatomical Mapping		Х		X			
Event Monitor				X**	X**		
Record DC Cardioversions Since Last Visit			Х	X	Х	Х	X
NYHA Classification	Х		Х	X	Х	Х	X
Fluoroscopic Examination of Diaphragm Motion						X**	
Objective Imaging Modality+	X ^{A+}		_				
Anticoagulation Monitoring		X**	X**	X**	X**	X**	X**
Adverse Events		Х	Х	Х	Х	Х	Х

^{*} Whichever is later

^{**} As needed

^A Within 1 month

 $^{^{+}}$ e.g., Transesophageal Echocardiogram (TEE), Transthoracic Echocardiogram (TTE), etc.

6. Risk Benefit Assessment

The Sponsor has conducted an analysis of the benefits and risks of the FARAPULSE Cardiac Ablation System and procedure. A detailed Risk Assessment has been completed, and the conclusion of this review is that this research study is justified because the overall potential benefit to the population outweighs its attendant risks.

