5.4 Trial Endpoints

5.4.1 Primary Safety Endpoint

A composite safety endpoint consisting of the proportion of subjects that experience one or more of the following serious adverse events (SAEs) related to the investigational procedure and/or device within 30 days of the PEF ablation procedure or hospital discharge, whichever is later, except as noted below:

- Cardiac death
- Stroke and/or transient ischemic attack (TIA)

- Myocardial infarction (MI)
- Excessive bleeding
- Atrio-esophageal fistula
- Persistent post-surgical phrenic nerve paralysis at 12 months
- Severe pulmonary vein stenosis (>70%)

Table 3 summarized the primary safety endpoint definitions.

Table 3: Primary Safety Endpoint Definitions

able 3: Primary Safety Endpoint Definitions					
Potential Serious					
Adverse Event	Definition				
Cardiac Death	Excludes all non-cardiac deaths.				
Stroke	A new focal neurological deficit of presumed vascular origin persisting more than 24 hours and with a neuro-imaging study that does not indicate a different etiology. All patients suspected of having a stroke will be evaluated by a neurologist and have appropriate imaging tests performed (CT or MRI) as determined by a neurologist.				
	 The 24-hour criterion is excluded if the subject undergoes cerebrovascular surgery or dies during the first 24 hours. 				
	This stroke definition includes subjects presenting with clinical signs and symptoms suggestive of subarachnoid hemorrhage, intracerebral hemorrhage, or cerebral infarction.				
	Stroke events in cases of blood disorders such as leukemia, and strokes secondary to trauma are excluded.				
Transient Ischemic Attack (TIA)	A focal ischemic neurological deficit of abrupt onset and of presumed vascular etiology that resolves completely within 24 hours of onset. All patients suspected of having a TIA will be evaluated by a neurologist and have appropriate imaging tests performed (CT or MRI) as determined by a neurologist.				

Potential Serious Adverse Event	Definition
Myocardial Infarction* (MI)	The presence of any one of the following criteria: 1) detection of ECG changes indicative of new ischemia (new ST-T changes or new LBBB), which persist for more than one hour; 2) development of new pathological Q waves on an ECG; 3) imaging evidence of new loss of viable myocardium or new regional wall motion abnormality.

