Excessive Bleeding*	Bleeding requiring re-operation or 2 units of PRBC transfusion within any 24 hours of the first 7 days following the index procedure.
Atrioesophageal Fistula	An atrial esophageal fistula is defined as a connection between the atrium and the lumen of the esophagus. Evidence supporting this diagnosis includes documentation of esophageal erosion combined with evidence of a fistulous connection to the atrium such as air emboli, an embolic event, or direct observation at the time of surgical repair. A CT scan or MRI scan are the most common methods of documentation of an atrial esophageal fistula.
Phrenic Nerve Paralysis*	Absent phrenic nerve function as assessed by a sniff test. A phrenic nerve paralysis is defined as permanent if it persists for 12 months or longer following ablation.
Pulmonary Vein Stenosis*	A reduction of the diameter of a PV or first generation PV branch. PV stenosis can be categorized as mild <50%, moderate 50%-70%, and severe ≥70% based on the percentage reduction in the diameter of the PV or PV branch. A severe PV stenosis should be considered a major complication of AF ablation.

^{* 2012} HRS/EHRA/ECAS Expert Consensus Statement on Catheter and Surgical Ablation of Atrial Fibrillation: Recommendations for Patient Selection, Procedural Techniques, Patient Management and Follow-up, Definitions, Endpoints, and Research Trial Design.

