5.5 Sample Size

Up to 25 subjects will be enrolled in this clinical trial.

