- Cardiac rhythm as determined by a 12-lead ECG at the time of the visit;
- Heart failure status as assessed by NYHA classification at the time of visit;
- Any hospital readmissions, including admission and discharge dates, since the previous visit; and
- Adverse events.
- If a subject is symptomatic for AF at the end of the blanking period, an event monitor will be provided to be used up to the 6-month follow-up visit to capture AF episodes.
- Patients will undergo an electro-anatomical remapping procedure to assess electrical isolation of the posterior left atrium and pulmonary veins. Any electrical gaps may be closed at the investigator's discretion using a commercially approved ablation device. This will consist of placement of catheters in the left atrium via femoral access and transeptal puncture using conventional electrophysiology techniques.
- Patients will undergo a cardiac CT or MRI scan at 3 months to assess the patency of the pulmonary veins.

5.13.6 6 Month Follow-up

Subjects will return for an office visit 6 months (180 days \pm 30 days) postablation treatment. At a minimum, the following data will be collected at 6 months:

- Use, changes in or discontinuation of anticoagulation, rate control and/or antiarrhythmic medications;
- Cardioversions since last visit;
- · Any additional ablation procedures performed;
- For subjects on anticoagulants, assessment of INR/PTT therapeutic levels (maintain as clinically indicated);
- Cardiac rhythm as determined by a 12-lead ECG at the time of the visit;
- Heart failure status as assessed by NYHA classification at the time of visit;
- Cardiac rhythm as determined by a 24-hour continuous ECG monitor following the visit for subjects in NSR at the time of the visit;
- Any hospital readmissions, including admission and discharge dates, since the previous visit; and
- Adverse events.

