7.1 General Statistical Considerations

The primary objective of this study is to characterize the safety and feasibility of the FARAPULSE Cardiac Ablation System in subjects with paroxysmal atrial fibrillation undergoing cardiac surgery.

The study is a feasibility study with no formal hypothesis testing and therefore no required sample size. Study results will be presented using descriptive statistics. Results from this study will be used to design additional clinical studies.

All subjects will be followed on an intent-to-treat basis. The device performance will be assessed based on a per-protocol analysis of the primary safety and feasibility endpoints and secondary efficacy endpoints. An intent-to-treat analysis, along with other secondary analyses, will also be completed and reported.

Demographic, baseline clinical and disease characteristics, procedural results and primary, secondary and all additional endpoints will be summarized using descriptive statistics.

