8.2 Adverse Event Reporting

All AEs, including all SAEs, will be monitored from the time of enrollment through discharge for this trial. All AEs must be recorded in the patient chart and Case Report Form (CRF). A description of the event, including the start date, resolution date, action taken and the outcome should be provided along with the Investigator's assessment of the relationship between the AE and the trial device.

All AEs should be followed until the event is resolved or judged to be chronically stable. The investigational site will provide relevant follow-up information to the Sponsor upon request.

The investigator should report to the Sponsor or its designee the following events, whether expected or not, in the corresponding sheet of the CRF, with the exception of AEs / SAEs detected before the patients has signed the patient consent form.

- AE
- SAF
- Device Deficiencies that did not but might have led to a SAE if:
 - Suitable action has not been taken or

- Intervention had not been made or
- If circumstances had been less fortunate
- New findings/updated in relation to already reported events.

If an AE / SAE is present at the beginning of study prior to the subject providing signed consent to participate in the study, only its worsening should be reported.

The investigator shall notify the sponsor and the CRO immediately and not later than 24 hours after the investigator has become aware of a SAE or device deficiency that might have led to a SAE via the Adverse Event Form of the CRF.

This reporting should be done by faxing completed CRF pages to the CRO:

CRO: MedPass International SAS

[contact]

Sponsor: FARAPULSE, Inc. [contact]

Email: [contact]
Contact: [name]

In the case of a SADE, when possible, the device involved in the failure or malfunction is to be returned to the Sponsor for analysis.

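### Phrenic nerve paralysis counts toward the primary safety composite, but the only diaphragm test is optional, untriggered and at 12 months, so silent cases can be missed

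*Combined protocol and SAP*

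**What the plan says.** Sections 5.4.1 and 7.7.1 list seven components of the primary safety composite. One is "Persistent post-surgical phrenic nerve paralysis at 12 months". Table 3 in 5.4.1 gives the case definition, "Absent phrenic nerve function as assessed by a sniff test", and the duration rule: "A phrenic nerve paralysis is defined as permanent if it persists for 12 months or longer following ablation".

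Table 4 in 5.16 has one row on the diaphragm, "Fluoroscopic Examination of Diaphragm Motion". Its only mark is in the 12-month column, with the footnote that makes the assessment conditional on need. No criterion for need is stated. The data lists for baseline, procedure, pre-discharge, 30 days, 3, 6 and 12 months (5.13) and for unscheduled visits (5.14) name neither a sniff test nor any other diaphragm examination.

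Section 7.4 rules out imputation and restricts analyses to the data available. It gives no rule for a subject who was never tested for one component. On size and inference: "Up to 25 subjects will be enrolled in this clinical trial", and "The study is a feasibility study with no formal hypothesis testing and therefore no required sample size".

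**The concern.** This component depends on a test: without a sniff test, nobody can meet the definition. A schedule that leaves the test optional, with no trigger, lets a subject finish the study with the component neither confirmed nor excluded. If such subjects are tallied as event-free, the reported count mixes those tested and found normal with those never tested.

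The error runs one way. Missed cases can only lower the composite. That matters here because the catheter surrounds the pulmonary veins (6.2), phrenic nerve injury is a named risk (3.4, 6.1.1), and 3.3 cites animal work in which the nerve was spared. The trial is first-in-man (7.2), and its results are meant to inform the design of later studies (7.1). A low count that reflects little testing could be read as human confirmation of the animal finding.

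**Working it through.** The plan states no event rate, power or expected count for this component, so there is no figure to reproduce. The check compares the definition with the schedule, then sizes the consequence.

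**1. Definition against schedule.** Table 3 needs a sniff test result and persistence to 12 months. Table 4 offers one conditional fluoroscopy at 12 months. Table 4 does not say that this fluoroscopy is the Table 3 sniff test; treating them as the same test is the charitable reading, and the gap exists on either reading.

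**2. Comparison with similar items in the plan.**
- Table 4 has two other rows marked as conditional. The event monitor has a trigger in 5.13.5 and 5.13.6.1 (symptomatic AF). Anticoagulation monitoring is listed in 5.13.2 and, in follow-up, tied to subjects on anticoagulants. The diaphragm row is the only conditional row with no counterpart in 5.13.
- Pulmonary vein stenosis, another component that depends on a test, is looked for in everyone: "Patients will undergo a cardiac CT or MRI scan at 3 months to assess the patency of the pulmonary veins" (5.13.5). The stated purpose of that scan is vein patency, so it does not stand in for a test of diaphragm function.

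**3. Effect on the chance of seeing no case.** Let p be the true rate of qualifying paralysis and s the share of true cases that get tested. The documents give neither, so both are assumptions shown over a range. With 25 subjects, P(no case recorded) = (1 − p·s)^25.

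| Assumed p | s = 100% | s = 50% | s = 25% | s = 0% |
|---|---|---|---|---|
| 2% | 60.3% | 77.8% | 88.2% | 100% |
| 5% | 27.7% | 53.1% | 73.0% | 100% |
| 10% | 7.2% | 27.7% | 53.1% | 100% |
| 20% | 0.4% | 7.2% | 27.7% | 100% |

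For example, at p = 10% and s = 25%: (1 − 0.025)^25 = 53.1%, against (1 − 0.10)^25 = 7.2% with full testing.

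**4. Effect of one missed case.** 1/25 = 4.0 percentage points on the composite. This requires 25 subjects in the denominator, an event that would be adjudicated serious and related, and no other component event in that subject.

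**5. Benchmark with complete testing.** The exact (Clopper-Pearson) two-sided 95% upper limit for zero events among n tested is 1 − 0.025^(1/n). For n = 25: 1 − 0.025^(1/25) = 13.7%. Even a fully tested zero leaves that much room.

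**The case against.** The strongest reply is that paralysis can reach the investigator without a scheduled test. Table 4 marks adverse events at every visit from the procedure on and NYHA class at every follow-up visit, and readmissions are collected in follow-up. Breathlessness could prompt the 12-month fluoroscopy. This stands for symptomatic cases. A reader might infer that a zero count is guaranteed; the documents do not support that. What remains are cases that are silent, or whose breathlessness is recorded as heart failure status, the heading under which NYHA is collected. The adverse event route is also less firm than Table 4 suggests, because 8.2 says "All AEs, including all SAEs, will be monitored from the time of enrollment through discharge for this trial". Those two passages need reconciling separately.

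Second, the composite counts only serious, related events, and 7.7.1 and 10.12 provide for adjudication. A silent one-sided paralysis might be judged a permanent impairment of a body function, but not automatically. That is why the 4 points is conditional.

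Third, the workflow documents cited in 5.13.2 are not available here and may contain an intra-operative check. Such a check could not establish status at 12 months.

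Fourth, this is one of seven components in a descriptive study. That lowers the stakes but does not remove the bias.

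Three further readings are tempting and should not be adopted.
- A reader might argue that the 365 ± 30 day window opens too early for a paralysis to have lasted 12 months. A visit inside that window is the ordinary reading of a 12-month endpoint.
- A reader might infer that a subject with paralysis could leave the study early. Section 5.15 withholds exit while a condition still needs follow-up, and 8.2 keeps adverse events under follow-up until they resolve or stabilise.
- A reader might compute a confidence limit from zero events among a handful tested on suspicion. The documents give no such number, and a group selected that way does not estimate the cohort rate.

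**Conclusion.** The concern holds. A primary safety component defined by a test has no systematic testing behind it, and nothing in the plan separates untested subjects from those tested and normal. The likely direction is under-counting, so the component and the composite can look safer than they are.

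The size is up to 4 percentage points on the composite per missed case, under the three conditions in step 4 of the working. How many cases would be missed cannot be derived from the documents: the paralysis rate, the share that is silent and the share that would be tested are all unstated. The probabilities in the table illustrate this dependence and are not predictions.

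A reader might infer that the plan would report 0 of 25 whatever the testing. It does not say so. Section 7.4 leaves the denominator open, and that silence is itself part of the problem.

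**What to change.** - **Table 4 and 5.13.5:** add a sniff test under fluoroscopy for every subject at the 3-month remap visit, before sedation. A paralysis caused by the index procedure and still present at 12 months should already be visible then.
- **Table 4, 12-month column, and 5.13.7:** replace the conditional mark with a required test for every subject with absent or reduced motion at 3 months, or with suspected paralysis at any visit. State that this test is the sniff test of Table 3.
- **7.4 and 7.7.1:** report the number of subjects tested beside the component count, and do not count untested subjects as confirmed event-free.

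Cost: a protocol amendment, a CRF field, brief added fluoroscopy at 3 months, and a 12-month test in what should be a few subjects. This assumes fluoroscopy is used for the transseptal puncture at the remap, which 5.13.5 does not state. One limit remains: without a baseline test, a pre-existing deficit cannot be fully separated from a new one.

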6.1 Risks

The risk profile associated with the FARAPULSE Cardiac Ablation System and the ablation procedure is expected to be minimal and consistent with other similar devices currently in clinical use during concomitant heart surgery.

6.1.1 Potential Adverse Events

The following anticipated events have been identified as possible complications of cardiac surgery and atrial fibrillation ablation procedures and these and others may be associated with the FARAPULSE Cardiac Ablation System:

- Air embolism
- Anemia
- Arrhythmia, potentially requiring cardioversion
- Arteriovenous fistulae
- Arrhythmias, possibly requiring a pacemaker
- Drug allergic reaction or side effects (e.g., from contrast, steroids, analgesics, anesthetics, anticoagulants, sedatives, etc.)
- Back pain
- Bed sores
- Bleeding, hematoma, hemorrhage or aneurysm at vascular access sites
- Coronary artery or vein injury
- Cardiac tamponade
- Cardiac arrest or cardiac failure
- Catheter entrapment
- Cardiogenic shock
- Congestive Heart failure
- Coupling across/crossing of unintended structures
- Death
- Esophageal injury
- Hemorrhage
- Hemodynamic compromise
- Hemopericardium
- Hemoperitoneum
- Hemothorax
- Hypotension
- Increased defibrillation threshold

- Local infection, systemic infection, and/or sepsis
- Myocardial infarction / transient ischemia
- Nerve damage
- Organ failure
- Pain
- Perforation (e.g., of diaphragm, heart, liver, lung, and/or vessels).
- Pericardial irritation
- Pericardial effusion
- Pericarditis
- Peritonitis
- Pneumomediastinum
- Pneumopericardium
- Pneumoperitoneum
- Pneumothorax
- Risk of cancer or birth defect/harm to fetus from x-ray exposure
- Skin burns/irritation from x-ray exposure
- Stroke/transient ischemic attack
- Surgical or open-heart surgery to remove retained catheter
- Thrombosis
- Thromboembolism
- Vessel damage, dissection, or occlusion.
- Phrenic nerve injury
- Conduction system injury resulting in sinus arrest or heart block, either transient or permanent

Concomitant medicinal and surgical treatments used during the procedure and follow-up phase of the clinical study include structural heart surgery for the index procedure, anticoagulation, and antiarrhythmic therapy. The FARAPULSE Cardiac Ablation System does not have any known interactions with these therapies.

There is no plan within this protocol to combine an endovascular ablative procedure with epicardial ablation using the FARAPULSE Cardiac Ablation System. However, if ablation using the FARAPULSE Cardiac Ablation System were ineffective and atrial fibrillation recurred, further ablative therapy may be pursued by the patient's physician outside the context of this study. When further ablation is done with electro-anatomical mapping, a further ablation procedure would not introduce any risks over and above those already inherent in a second ablation procedure whether done through the epicardium or the endocardium. The risks of any second ablative procedure are the same as the risks summarized above.

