5.3 Trial Design

5.3.1 Description of Trial Design

Prospective, single-arm, multi-center feasibility trial. Subjects will be consented to undergo surgical PEF ablation using the FARAPULSE Cardiac Ablation System concomitant to heart surgery. Subjects will be followed at 30 days, 3 months, 6 months and 12 months following the index surgical procedure with a blanking period for recurrent atrial fibrillation or atrial tachycardia of 3 months following the index surgical procedure.

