5.13.3 Pre-Discharge

Prior to hospital discharge the following data will be collected:

- Use, changes in or discontinuation of anticoagulation, rate control and/or antiarrhythmic medications;
- Cardioversion(s) since surgery;
- For subjects on warfarin, assessment of INR therapeutic levels (maintain as clinically indicated);
- For subjects on dabigatran, perform a PTT and, if required, a thrombin time (Section 4.7.2.7 Anticoagulation Regimen);

- Cardiac rhythm as determined by a 12-lead ECG on day of hospital discharge;
- Heart failure status as assessed by NYHA classification on day of hospital discharge; and Adverse Events.

5.13.4 1 Month Follow-Up

Discharged subjects will return for an office visit 30 days (± 7 days) postablation treatment. Subjects that continue to be hospitalized 30 days postablation will have their 30-Day Follow-Up assessment performed at discharge. At a minimum, the following data will be collected at 30 Day Follow-Up visit:

- Use, changes in or discontinuation of anticoagulation, rate control and/or antiarrhythmic medications;
- Cardioversions since last visit;
- For subjects on anticoagulants, assessment of INR/PTT therapeutic levels (maintain as clinically indicated):
- Cardiac rhythm as determined by a 12-lead ECG at the time of the visit;
- Heart failure status as assessed by NYHA classification at the time of visit;
- Any hospital readmissions, including admission and discharge dates, since discharge from the original procedure; and

5.13.5 3 Month Follow-Up

Subjects will return for an office visit at the end of the blanking period (90 days \pm 14 days post-ablation treatment). During the blanking period, any recurrence of AF will be documented; however, recurrences of AF, AFL or AT during this time will not be considered therapeutic treatment failures. Subjects are not permitted to undergo repeat ablation during the blanking period. If a repeat ablation procedure is performed during this time, the subjects will be considered a therapeutic treatment failure and exited from the study.

At a minimum, the following data will be collected at the end of the blanking period follow-up visit:

- Use, changes in or discontinuation of anticoagulation, rate control and/or antiarrhythmic medications;
- Cardioversions since last visit;
- Any additional ablation procedures performed;
- For subjects on anticoagulants, assessment of INR/PTT therapeutic levels (maintain as clinically indicated);

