7.4 Imputation for Missing Data

Imputations for missing data in (e.g., withdrawn subjects, loss to follow-up, missing data) will not be performed. Analyses will be performed with all available data only.

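### Section 5.13.5 permits catheter gap closure at the 3-month remap but could also exit the subject for it, and Section 6.1.1 places such ablation outside the study

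*Combined protocol and SAP*

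**What the plan says.** **Permission.** Section 5.13.5 (3 Month Follow-Up) requires an electro-anatomical remap at the visit on day 90 ± 14. The investigator may choose to close a gap found there, which the text describes as done "using a commercially approved ablation device. This will consist of placement of catheters in the left atrium via femoral access"; the route is transseptal.

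**Ban and exit.** Earlier in the same section: "Subjects are not permitted to undergo repeat ablation during the blanking period". The consequence follows: "If a repeat ablation procedure is performed during this time, the subjects will be considered a therapeutic treatment failure and exited from the study".

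**End of blanking.** Section 5.3.1 defines "a blanking period for recurrent atrial fibrillation or atrial tachycardia of 3 months following the index surgical procedure". Section 5.13.5 instead places the visit at the end of blanking, and Table 4 (Section 5.16) heads the column "3 Month (End of Blanking Period").

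**Risk section.** Section 6.1.1 states: "There is no plan within this protocol to combine an endovascular ablative procedure with epicardial ablation using the FARAPULSE Cardiac Ablation System". It then describes further ablation as something the patient's own physician may pursue outside the study if AF recurs.

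**Analysis.** Section 7.1: "All subjects will be followed on an intent-to-treat basis". Section 7.4 rules out imputation: "Analyses will be performed with all available data only". Section 5.4.5 scores a repeat ablation at any time up to Month 12 as a therapeutic failure and does not mention exit.

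**The concern.** Section 5.13.5 gives a permission and a prohibition that can meet at one visit. Whether they do depends on two things left undefined: whether closing a gap at the remap is a repeat ablation, and whether blanking ends on a fixed day or at the visit. Two sites could treat the same subject differently and both point to the text.

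The subjects exposed to exit are those with a mapped gap, that is, those in whom the lesion did not hold. In a first-in-man study of up to 25 subjects they are an informative group. With available-data analysis, an exited subject drops out of the two later SAE intervals (Sections 5.4.2 and 7.7.2).

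For closed subjects who stay, the interval SAE endpoint counts every SAE. Events from the catheter touch-up then enter the same proportion as events after the study device alone. Adjudication of device and procedure relatedness (Section 7.7.1) helps, but no listing by closure status is planned.

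The second matter is the mismatch in Section 6.1.1, which does not acknowledge that an endovascular ablation may take place inside the study.

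**Working it through.** The plan gives no gap rate, closure rate or hypothesis test, so there is no figure of its own to reproduce. The check compares the text and counts calendar days.

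**Inputs**
- Month 3 visit: day 90 ± 14 (Section 5.13.5, Table 4).
- Blanking: 3 months from the index procedure (Section 5.3.1), taken here as 90 days (assumption).
- Month 12 visit: nominal day 365 (Table 4).
- SAE intervals: four, the last two starting at the Month 3 and Month 6 visits (Section 5.4.2).
- Enrolment: up to 25 (Section 5.5).

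**1. Visit window.** 90 − 14 = 76 and 90 + 14 = 104. Length = 104 − 76 + 1 = 29 days.

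**2. Overlap with blanking**
- Blanking ends at the visit: 0 of 29 days.
- Blanking ends on day 90: days 76 to 89, so 89 − 76 + 1 = 14 of 29 (48%). Counting day 90 itself as blanked gives 15 of 29 (52%).

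These are calendar days, not probabilities that a visit falls there.

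**3. Follow-up lost on exit**
- Day 76: 365 − 76 = 289 days; 289/365 = 79.2%.
- Day 89: 365 − 89 = 276 days; 276/365 = 75.6%.

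The Month 3–6 and Month 6–12 intervals are lost, 2 of 4.

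**4. Effect of one exit on an interval SAE proportion.** Illustration only, assuming 5/25 = 20.0% with full follow-up:
- Lost subject would have been event-free: 5/24 = 20.8% (+0.8 points).
- Lost subject would have had an event: 4/24 = 16.7% (−3.3 points).

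**5. Number affected.** Without a closure rate it could be anything from 0 to 25.

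**6. Section 6.1.1 beside Section 5.13.5**
- Who acts: the patient's physician (6.1.1); the investigator (5.13.5).
- Trigger: ineffective ablation with recurrent AF (6.1.1); a mapped gap, with or without AF (5.13.5).
- Setting: outside the study (6.1.1); a required study visit (5.13.5).

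The two descriptions differ on all three.

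**The case against.** **The natural reading has no overlap.** Section 5.13.5 and Table 4 both equate the visit with the end of blanking, and symptoms at the end of blanking are assessed at that same visit. A specific permission to close gaps should also prevail over a general ban, since permitting an act that triggers exit defeats its purpose. This is a fair reading and probably the intended one. But Section 5.3.1 counts blanking from the index procedure, and no text says which reading holds or exempts closure from the ban.

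**The risks are already covered.** This stands. Section 6.1.1 lists access-site bleeding, tamponade, perforation and embolic events, and says any second ablation, epicardial or endocardial, carries the same risks. A reader might infer that catheter risks were left out; the documents do not support that. Only the statement about setting is wrong.

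**The effect is small and the study descriptive.** This also stands. At 5/25 the exact 95% interval runs from about 7% to 41%, far wider than the shift from one exit. No test is affected.

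**Stronger inferences that the documents do not support**
- *The 12-month phrenic component would be missing for an exited subject.* A post-surgical palsy would normally be an ongoing adverse event by days 76 to 89. Sections 5.10 and 8.2 provide for following such events until resolved or stable. The 12-month fluoroscopy in Table 4 is only as needed. At most, a palsy not recognised before exit, or judged stable before Month 12, could be lost.
- *Closure inflates therapeutic success.* On its plain wording Section 5.4.5 makes closure a failure.
- *Technical success could be scored after closure.* Sections 5.4.4 and 5.13.5 make the remap the assessment, with closure following from what it finds, so the order is implied.

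**Conclusion.** The point holds in a limited form. Section 5.13.5 does not settle whether closing a gap at the remap exits the subject. If blanking ends on day 90 and closure counts as repeat ablation, 14 of 29 window days fall under both rules. A subject exited on those days loses 76% to 79% of the year and two of four SAE intervals. That conflicts with the intent-to-treat follow-up in Section 7.1, and follow-up of adverse events already ongoing at withdrawal would not capture new ones. If blanking ends at the visit, the overlap is zero and only the lack of clarity remains.

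Separately, Section 6.1.1 misdescribes where further ablation may take place.

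The primary feasibility endpoint is unaffected. The consequence is for interpretation of later safety follow-up. The change should be made because it is cheap and decides whether subjects with failed lesions stay under observation. The result rests on taking 3 months as 90 days; the 20% SAE proportion is an illustration, not an expectation.

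**What to change.** - **Section 5.13.5:** state that gap closure at the 3-month remap is a therapeutic failure under Section 5.4.5, does not trigger the blanking-period ban or study exit, and that the subject is followed to Month 12.
- **Section 6.1.1:** state that optional gap closure may take place within the study at the 3-month remap, and that the second-ablation risks already listed apply to it.
- **Reporting:** give the number of subjects closed, and list post-remap SAEs by closure status.

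The cost is amendment wording, one CRF flag for remap closure and one small descriptive listing. Additional ablations are already recorded at Months 3, 6 and 12, so the flag only separates remap closure from other procedures. Cells will be small, so the listing should stay descriptive.
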